11.0 Provisions to Monitor the Data to Ensure the Safety of Subjects*

The study will be monitored to ensure that it is conducted in conformance with the monitoring plan to assess continued compliance with the protocol and recognized Good Clinical Practices (GCP).

The PI ([name]) will verify that study records are adequately maintained, that data are reported in a satisfactory manner with respect to timeliness, adequacy, and accuracy, and that the investigative team continues to have sufficient staff and facilities to conduct the study safely and effectively.

Data Safety and Monitoring Plan

PROTOCOL TITLE: *Health Through Activity: A pilot study of a rehabilitation intervention for people living with multiple myeloma*

The following procedures will be followed to ensure the safety of study participants and the validity and integrity of data.

- **Range of Safety Reporting:** Drs. [name] and [name] will debrief (with the interventionists and/or observing students at the IMPACT Practice Center) after every session to explore and document the session content and any safety concerns. This includes reports of Adverse Events noted by the interventionists or the research coordinator.
- **Data Repository:** The research team has established procedures for data collection and management. [name] will oversee all aspects of data collection for the study, and the research coordinator will have the operational responsibility of data management. Specifically, the research team will develop a study-specific data management protocol and standard operating procedures for the creation and testing of all study forms, data collection, quality control, and data extraction. All data management activities will utilize REDCap.
- **Serious Adverse Events (SAEs):** Given that this is a rehabilitation study in a population at risk for disease progression and death due to their medical condition (unrelated to study procedures), we do not expect any SAEs to be related to the study. Thus, SAEs will not be reported to the IRB, unless they are potentially related to the study procedures. Any SAEs related to the study procedures should be entered into the Electronic Data Capture (EDC) system within three (3) business days of the site becoming aware of the event.. If a SAE is reported, the MGH research team shall immediately conduct an evaluation of the SAE and will make a determination as to whether it meets the criteria for definition and for reporting to the IRB. Any reportable SAEs will be reported to the IRB as soon as possible, but in no event later than ten (10) working days after becoming aware of the event.
- **Non-Serious AE:** The research team will review monthly summary reports of the numbers and rates of AEs by treatment group and study site. These reports will include types of events, severity, and treatment phase.
- Relationship of SAE and AEs: the research team will assess the potential relationship of AEs or SAEs to the HTA intervention and classify the causality of the event according to the following definitions
 - **Definitely Related:** An AE that has a strong causal relationship. An AE that follows a strong temporal relationship, follows a known response pattern, and cannot reasonably be explained by known characteristics of the subject's clinical state or other therapies.
 - **Probably Related:** An AE that potentially has a causal relationship. The AE has a reasonable temporal relationship and alternative etiology is less likely compared to the potential relationship to the HTA program.

- **Possibly Related:** An AE that potentially has a causal relationship. The AE has a reasonable temporal relationship to the use of the investigational mobile apps but alternative etiology is equally likely compared to the potential relationship to the HTA program.
- **Not Related:** An AE without any apparent causal relationship. The AE is due to the underlying disease state or is due to concomitant medication or therapy not related to the HTA program.
- **Unknown Relationship:** If the AE cannot be determined to have a causal relationship, it will be classified as unknown.

- **Other Safety-Related Reports:** The research team will review weekly summary reports of treatment retention and reasons for dropout.

Monitoring of Data Quality by the Research Team:

The research team (at each participating institution) will review the following items on weekly basis to ensure data quality and completeness:

- Total enrollment compared with anticipated enrollment
- Number of ineligible patients registered
- Proportion of missing participant-reported outcomes
- Proportion of other missing data
- Number of participants lost to follow-up
- Number of participants completing the study

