2.0 Background

People living with multiple myeloma are at risk of developing disability

Multiple myeloma (MM) is a chronic malignancy of the plasma cells in bone marrow and is the second most common hematological cancer.[1] Most commonly diagnosed in people over the age of 65,[2] MM has a five-year relative survival rate of 58%. [3] Though considered incurable, more individuals are living with MM as a chronic health condition for years due to advancements in therapeutic approaches to managing MM.[4]

Many people living with MM experience distressing symptoms which limit their ability to engage in meaningful activities. While the impact of MM is variable, the most prevalent symptoms experienced are fatigue, pain, insomnia, and peripheral neuropathy.[1, 5-8] Additionally, up to 80% of individuals with MM develop osteolytic skeletal lesions which can cause bone pain and pathologic fractures.[1, 9] These sequelae of MM and its treatments, along with commonly reported symptoms of anxiety and depression,[10] may result in decreased physical functioning, limited health-related quality of life, and difficulty engaging in activities related to valued roles.[1, 5, 6] Furthermore, people living with MM are at an increased risk of falling,[11] and many fear pain or injury (e.g., pathological fractures) which can lead to avoidance of physical activity and exercise. Taken together, people with MM are at high risk for developing disability, i.e., a perceived limitation in and reduced frequency of activity engagement.[12-14]

Rehabilitation interventions to reduce disability

PROTOCOL TITLE: *Health Through Activity: A pilot study of a rehabilitation intervention for people living with multiple myeloma*

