13.0 Risks to Subjects

There are three potential risks involved in this study: (1) the risk of hurting oneself when trying to exercise or increase activity level (e.g., falling while exercising or performing home management tasks); (2) the risk of distress while talking about disability and quality of life; and (3) risk of loss of confidentiality. The level of risk is generally low and strategies to minimize risks are incorporated into the HTA treatment manual and are addressed below.

Risk of injury: The goal of the HTA intervention is to reduce disability by fostering engagement in exercise and valued activity. The intervention teaches participants to change aspects about themselves, the task, or how it is performed to engage in valued activities. Regarding the risk of injury, the HTA program includes action planning to increase the safety and success of activity engagement to minimize the chances of this risk. Furthermore, we will follow clinical practice guidelines that foster safe exercise engagement and delineate contraindications for exercise. Individualized exercise instructions will minimize risk of injury by emphasizing postural alignment, controlled movements, utilization of proper technique, fall risk reduction, and by considering participants' individual risk factors (e.g., lytic lesion location, peripheral neuropathy).[18, 33] Patient educational materials will emphasize how to recognize abnormal responses to exercise and reasons to cease exercise and seek medical attention. Bidirectional communication with the participants' medical team will ensure identification of and consensus regarding any necessary precautions or contraindications to exercise. The therapists are knowledgeable in site-specific procedures to summon emergency medical help. If a participant sustains an injury while enrolled in the study, they will be assisted and instructed to seek medical attention commensurate to their injury including but not limited to presenting to the emergency room and/or following up with their oncologist for further evaluation. For virtual study visits, participants will be provided with a virtual handout depicting each exercise and the physical therapist will provide specific exercise instructions and explicit guidance to maintain safety

PROTOCOL TITLE: *Health Through Activity: A pilot study of a rehabilitation intervention for people living with multiple myeloma*

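### Section 11.0 makes EDC entry of SAEs depend on relatedness, uses a narrower trigger than for IRB reporting, and assigns Unknown Relationship to neither

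*Combined protocol and SAP*

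**What the plan says.** The rules are in the Data Safety and Monitoring Plan of Section 11.0.

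- **Premise.** Because participants are at risk of progression and death from their disease, "we do not expect any SAEs to be related to the study".
- **IRB trigger.** "SAEs will not be reported to the IRB, unless they are potentially related to the study procedures". The deadline for reportable events is "in no event later than ten (10) working days after becoming aware of the event".
- **Database trigger.** "Any SAEs related to the study procedures should be entered into the Electronic Data Capture (EDC) system within three (3) business days", counted from the site becoming aware.
- **Evaluation.** Once an SAE has been reported, the team evaluates it and "will make a determination as to whether it meets the criteria for definition and for reporting to the IRB".
- **Causality scale.** There are five classes: Definitely, Probably, Possibly, Not Related and Unknown. For the last, "If the AE cannot be determined to have a causal relationship, it will be classified as unknown".
- **Summaries.** Monthly reports of adverse event numbers and rates are described under the Non-Serious AE bullet.
- **Debriefs.** After every session, safety concerns are documented, including adverse events noted by the interventionists or the research coordinator.

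**The concern.** A safety database is useful if events go in first and are attributed afterwards. Read literally, Section 11.0 reverses that order for SAEs: the only entry rule applies to events that are related, so someone must make the causality call before the duty to enter exists. If the call is wrong, the database need not hold the event that would let anyone see it.

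This matters here because disease and intervention can be competing explanations for the same event. Section 13.0 lists first among the study risks "the risk of hurting oneself when trying to exercise or increase activity level (e.g., falling while exercising or performing home management tasks". Section 2.0 says that "up to 80% of individuals with MM develop osteolytic skeletal lesions which can cause bone pain and pathologic fractures" and that these patients are at increased risk of falling. The premise that no SAE will be related does not sit easily beside those statements. The study is meant to prepare for efficacy testing (Sections 2.0 and 14.0), and a complete SAE list with attribution open to review is one thing a successor trial would want from it.

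**Working it through.** The plan gives no figure to reproduce, and no calculation applies. The check sets the rules side by side.

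**Step 1. The two triggers.** The IRB sentence says potentially related; the EDC sentence that follows says related. The definitions of *Probably* and *Possibly Related* both describe a potential causal relationship, so both meet the IRB trigger. Whether they meet the EDC trigger depends on whether related is read strictly or as shorthand.

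**Step 2. Stated duty for an SAE in each class.**

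| Class | EDC entry in 3 business days | IRB report |
|---|---|---|
| Definitely Related | Yes | Yes |
| Probably Related | Unclear | Yes |
| Possibly Related | Unclear | Yes |
| Not Related | No | No |
| Unknown Relationship | Not assigned | Not assigned |

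One class of five has both duties beyond doubt. Two can require an IRB report while the entry duty is unclear. One has neither duty, and one is unassigned. No sentence requires entry of all SAEs.

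**Step 3. Could another route put the remaining SAEs in the database?**

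- *Session debrief (Section 11.0).* It has no relatedness filter, but it follows a session. An event that stops attendance produces no session to debrief, and none is described after session 6.
- *Causality classification (Section 11.0).* It covers adverse events and SAEs alike, but no form, deadline or destination is stated.
- *Monthly summary (Section 11.0).* It is placed under Non-Serious AE.
- *Weekly data-quality list (Section 11.0).* It has no SAE item.
- *Weekly review of dropout reasons (Section 11.0).* Section 12.1 keeps participants in the study when they are advised to stop exercise, unless they ask to leave, so an injured participant need not appear as a dropout.
- *Assessment schedule (Section 8.3, Data Collection).* The table has no adverse event item at any time point. Time 3 is six weeks after completion, and the coordinator collects data by telephone at Times 2 and 3 with no listed question on events.

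**Step 4. Illustration.** Suppose a participant is hospitalised four weeks after session 6 and the team attributes this to myeloma. The event is *Not Related*: no EDC entry is required, no IRB report is due, no session debrief follows, no scheduled instrument asks about it, and the monthly summary as placed does not cover it. If the team hears of it, it must classify it, but nothing says where that classification is kept.

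**The case against.** The strongest reply is that this is a wording gap inside a plan that already documents safety broadly. Much of that stands.

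- A reader might infer that such SAEs leave no required record at all. The documents do not support that. Debriefs after every session document safety concerns without asking about relatedness, classification covers all adverse events and SAEs, and Section 12.1 counts suspensions of exercise. What is missing is a required database entry, chiefly for events that are not picked up at a session.
- A reader might infer that a fall or fracture during home exercise would escape the IRB. If timing is reasonable and disease is an equally likely cause, the event fits *Possibly Related* and is reportable. Nor do the documents show that such events would mostly be classed *Not Related* or *Unknown*.
- A reader might infer that *Unknown* is excluded from reporting. It is unassigned. An event of undetermined cause can reasonably be read as potentially related, but two coordinators could read it differently.
- A reader might try to size the gap from supervised session time, or from the share of the sample that one event represents. Home exercise hours are not given, and no SAE proportion is an endpoint or feasibility threshold, so neither figure measures the defect.
- Keeping unrelated SAEs out of IRB reporting is a reasoned choice in this population, and nothing here disputes it.
- The word related may be shorthand for potentially related, and the evaluation step does come after a report. That would settle *Probably* and *Possibly Related*, but would still leave *Not Related* SAEs without an entry duty and *Unknown* without a stated one.
- Section 11.0 defers form and collection detail to a data management protocol and operating procedures that are not among the documents. They may fill the gap, but the protocol's own rule would still be filtered by relatedness.

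**Conclusion.** The point stands as one about database capture and consistent triggers. As written, an SAE judged unrelated or unknown need not be in the study database, so a complete SAE count is not assured and attribution cannot reliably be re-checked there. The gap is widest in the six weeks from completion to Time 3 and for events that end attendance.

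The size is structural: four of the five causality classes lack a clear entry duty on a strict reading, and two on the more generous one. The documents give no SAE rate, so the number of events affected cannot be estimated. With at most 20 participants it would be small in absolute terms. No feasibility endpoint or threshold is affected.

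This rests on two assumptions: that the protocol text governs, and that the unseen operating procedures do not already require entry of every SAE. The section also refers to mobile apps, treatment groups and participating institutions, although this is a single-arm study recruiting at one centre with no app. That suggests text carried over from another trial rather than a deliberate restriction, but it is an inference. The change is worth making because it is cheap.

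**What to change.** Amend Section 11.0 in four places.

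1. State that all SAEs from the first study visit to Time 3 are entered in REDCap within the existing three business days of awareness, whatever their relationship, and that causality is assigned afterwards.
2. Use potentially related consistently wherever relatedness is a trigger.
3. State that *Unknown Relationship* is handled as potentially related for the IRB determination, subject to the IRB's own rules, which the documents do not give.
4. Include SAEs in the monthly summary.

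Unrelated SAEs stay outside IRB reporting, as the plan intends.

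The cost is a short amendment, using a system the plan already names for all data management. A few disease-related SAEs will have to be entered, and an occasional extra event will go to IRB review, among at most 20 participants. No eligibility, intervention or exercise rule changes.

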12.0 Withdrawal of Subjects

12.1. When and How to Withdraw Subjects. Throughout the study, participants will be aware that their participation in the study is voluntary. In general, participants will be focusing on engaging in activities of their choosing with the goal setting and action planning involving detailed ways to maximize the safety of activity engagement and minimize chance of injury, e.g., risk of falling during exercise. As such, there are very few times when it would be necessary to withdraw a participant from the study. That said, there are times when exercise is contraindicated such as in the presence of unstable bony metastases, increased pain (beyond normal expected response to exercise), altered neurologic presentation (e.g., diminished reflexes, bowel/bladder changes), or myelosuppression (e.g., thrombocytopenia/anemia below thresholds for safe exercise).[18, 33, 60, 61] Should those situations occur, participants will be advised to discontinue exercise until the situation resolves. Monitoring the number of times that exercise recommendations need to be suspended will inform us as to the feasibility and acceptability of the intervention for this population. As such, participants may be advised to discontinue exercise, but will not be withdrawn from the study unless they ask to be withdrawn.

PROTOCOL TITLE: *Health Through Activity: A pilot study of a rehabilitation intervention for people living with multiple myeloma*

Our team continues to attempt to contact participants for each session and study assessment unless and until they ask us to stop/express the desire to withdraw. Each study contact is an extension of informed consent where participants are told what is occurring, what happens next, and that their participation is voluntary. When we are unable to reach participants by telephone for at least 30 days we send a letter conveying our attempts to reach them and ask them to contact us to continue with study activities or withdraw, as they prefer.

12.2. Data Collection and Follow-up for Withdrawn Subjects. Participants who choose to withdraw from the intervention will be asked if they are amenable to continued participation in the data collection with the research coordinator or if they wish to completely withdraw from the study. The research coordinator will inform the participant that either choice is acceptable and completely up to them.

13.0 Risks to Subjects

There are three potential risks involved in this study: (1) the risk of hurting oneself when trying to exercise or increase activity level (e.g., falling while exercising or performing home management tasks); (2) the risk of distress while talking about disability and quality of life; and (3) risk of loss of confidentiality. The level of risk is generally low and strategies to minimize risks are incorporated into the HTA treatment manual and are addressed below.

Risk of injury: The goal of the HTA intervention is to reduce disability by fostering engagement in exercise and valued activity. The intervention teaches participants to change aspects about themselves, the task, or how it is performed to engage in valued activities. Regarding the risk of injury, the HTA program includes action planning to increase the safety and success of activity engagement to minimize the chances of this risk. Furthermore, we will follow clinical practice guidelines that foster safe exercise engagement and delineate contraindications for exercise. Individualized exercise instructions will minimize risk of injury by emphasizing postural alignment, controlled movements, utilization of proper technique, fall risk reduction, and by considering participants' individual risk factors (e.g., lytic lesion location, peripheral neuropathy).[18, 33] Patient educational materials will emphasize how to recognize abnormal responses to exercise and reasons to cease exercise and seek medical attention. Bidirectional communication with the participants' medical team will ensure identification of and consensus regarding any necessary precautions or contraindications to exercise. The therapists are knowledgeable in site-specific procedures to summon emergency medical help. If a participant sustains an injury while enrolled in the study, they will be assisted and instructed to seek medical attention commensurate to their injury including but not limited to presenting to the emergency room and/or following up with their oncologist for further evaluation. For virtual study visits, participants will be provided with a virtual handout depicting each exercise and the physical therapist will provide specific exercise instructions and explicit guidance to maintain safety

PROTOCOL TITLE: *Health Through Activity: A pilot study of a rehabilitation intervention for people living with multiple myeloma*

within the participant's environment (e.g., clearing space to avoid tripping on clutter, standing next to a countertop to maintain balance). As with in-person study visits, exercises will be based on the results of the participant's physical examination during the in-person Study Visit 1, reducing the chance of prescribing exercises that are beyond their capacity or that will jeopardize their safety. Regarding risk of injury during a virtual study visit, therapists will adhere to IMPACT Practice Center policies regarding recognizing and responding to health emergencies during telehealth care. Therapists will confirm and document the participant's location at each visit in case emergency services need to be summoned. If an injury occurs and it is determined that emergency care is required, the therapists will call 911 or, if others are present with the participant at their location, will advise the individual present to call 911. Therapists will help provide the 911 operator with necessary information and will stay on the virtual visit until emergency medical services arrive at the participant's location.

Risk of distress: This is somewhat of a self-correcting problem because the objective of HTA is to provide a structured process to help people find ways to increase activity engagement. The interventionists are trained to validate feelings of frustration and distress while re-directing the participant to actionable ways to make immediate progress. Likewise, the research coordinators who administer the outcome assessment are also trained in listening for signals of distress (e.g., long pauses, weeping) and are trained handle distress tactfully (e.g., do not indicate verbally or non-verbally that they are uncomfortable with participant distress) and to remind the participants that they can discontinue the surveys at any time. The outcome assessments of disability, activity engagement and quality of life do not contain many emotionally charged items and we find that most participants voice an appreciation for being asked to consider these aspects of their lives as opposed to being upset by them. If a participant becomes very upset, study staff will help them find a counselor and/or provide them with mental health crisis resources available through MGB and the Massachusetts Department of Mental Health.

Risk of privacy loss: Finally, to address a low-level risk of loss of privacy, participant confidentiality will be strictly protected. Hard copies of data will be maintained in locked files that can only be accessed by study personnel. Data forms will be identified using an identification (ID) number only. Access to the list cross-tabulating ID numbers with participant names will be kept in a password-protected data file following the RISO recommendations. All computer systems and programs will be password protected, and all electronic communications of study and other confidential information will be encrypted. Good computer security practice (shutting down computers after work hours, restricting physical access to machines, prohibition of password sharing) will be required of all study personnel. Virus protection software is installed on each study computer. The virus detection tools are used, maintained, audited and, if necessary, updated on all computers and pathways into the system. Redundant backups allow for quick restoration of data in the unlikely event that a hardware failure or security breach occurs.

PROTOCOL TITLE: *Health Through Activity: A pilot study of a rehabilitation intervention for people living with multiple myeloma*

